3.5.6 Discussion and Rationale for Current Study

In June, 2006, Stemline Therapeutics, Inc. ("Stemline") in-licensed development and commercialization rights for DT388IL3 and designated the product SL-401. The SL-401 DP to be utilized in the current study (conducted under a new IND) will be manufactured using a commercial-scale process.

IL-3R-rich pDCs have been demonstrated to be increased in the BM of patients with MM and contribute to disease aggressiveness and resistance to treatment (Chauhan 2009). pDC-MM cell interactions are associated with enhanced production of IL-3, which in turn, enhances MM cell growth and pDC survival. SL-401 has been shown to significantly decrease the viability of pDCs, even at low concentrations (IC₅₀, 14.6 pM). SL-401 also decreases the viability of MM

cells at clinically achievable concentrations without significantly affecting the viability of normal peripheral blood mononuclear cells (PBMCs). Co-culture of pDCs with MM cells triggers tumor growth, which, in turn, is blocked by low concentrations of SL-401. MM patient-derived pDCs also induces proliferation of MM cell lines and primary MM cells sampled from patients. Additionally, SL-401 has been shown to inhibit pDC-triggered MM cell growth, even in patients whose disease had progressed while receiving bortezomib, dexamethasone, and/or lenalidomide. SL-401 also blocked pDC-induced growth of dexamethasone-, doxorubicin- or melphalan-resistant MM cell lines. Additionally, combination of SL-401 with bortezomib, melphalan, or lenalidomide showed synergistic anti-MM activity. These preclinical results support the notion of directly targeting pDCs and inhibiting pDC-MM interactions, as well as targeting MM cells, in novel therapeutic strategies with SL-401 to enhance MM cytotoxicity, overcome drug-resistance, and improve overall patient outcome (Chauhan et al. 2013).

The prior clinical results with SL-401 indicate that the agent can be safely administered to patients with *de novo* AML, relapsed/refractory AML, or BPDCN, with clinical benefit in terms of disease response and extended survival. While 16.6 μg/kg/day for 5 consecutive days was determined to be the MTD and a safe starting dose for subsequent studies, the starting dose selected for this phase 1/2 study, 7 μg/kg/day (the lowest tested dose for this regimen (7.07 μg/kg/day in Study 50047), will allow for an initial (3 dose level) dose escalation/confirmation stage to an expected maximum tested dose (12 μg/kg/day) that is anticipated to have the most favorable risk/benefit profile.

The SL-401 drug product used in the current study will be manufactured using a commercialscale process that will provide study material for all pivotal studies. The current study will generate clinical experience in which administration of multiple cycles of SL-401 can be evaluated in combination with POM/DEX in a patient population that may derive clinical benefit.

The LFT and albumin findings from SL-401 in Study 50047 indicate that most patients with clinically meaningful changes in these parameters following administration of SL-401 would be expected to recover to near baseline levels by 3-4 weeks following the initiation of therapy. These results therefore support administration of cycles every 3 weeks with the allowance to delay the start of a subsequent cycle to allow toxicity resolution. In this study, a 28-day schedule will be used in combination with POM and DEX to allow for additional time for recovery from potential toxicity. Capillary leak syndrome was the principal DLT in Study 50047, but was a relatively uncommon event at doses at or below the MTD. Similarly, capillary leak syndrome is an event associated with treatment with approved doses of denileukin diftitox (Ontak®), a Food and Drug Administration (FDA)-approved treatment for patients with persistent or recurrent cutaneous T-cell lymphoma whose malignant cells express the IL-2 receptor. Treatment of patients with SL-401 at doses below those in which multiple cases of severe capillary leak syndrome were observed in Study 50047 is one element by which the risk of this SL-401 associated toxicity will be minimized in the current study.

During Study 50047, risk mitigation measures for capillary leak were implemented. These included premedication (e.g., an H₁-histamine antagonist, acetaminophen, and a corticosteroid); administration of IV albumin if serum albumin decreased to < 3 g/dL; and a diuretic regimen (e.g., furosemide) if patients experienced > 10% weight gain (with no hypotension) concurrent with the administration of a basal parenteral hydration to maintain intravascular volume. In the peri-treatment period, vital signs, weight, serum electrolytes, and albumin were monitored. Similar measures have been incorporated into the current study, as described in Section 7.3.2. Additional precautions, including a requirement that subjects have a normal cardiac ejection fraction at study entry, and requiring withholding of treatment in the setting of albumin reductions or weight increases during the dosing period, similar to recommendations concerning the optimal administration of denileukin diffitox, have also been implemented (McCann et al. 2012, Olsen et al. 2001, Prince et al 2009).

4 Study Objectives

4.1 Primary Objectives

- To evaluate the safety of single agent SL-401 in an initial run-in cycle in patients with MM.
- To determine the MTD or the maximum tested dose of SL-401 given in combination with POM/DEX for the treatment of relapsed or RRMM.
- To characterize the safety and tolerability profiles of SL-401 in combination with POM/DEX at the MTD.

4.2 Secondary Objectives

- To evaluate immunogenicity of SL-401 in combination with POM/DEX.
- To evaluate the PK of SL-401 as single agent and when administered in combination.
- To evaluate the activity of the combination of SL-401/POM/DEX regimen in terms of:
 - Overall response rate (CR+ very good partial response [VGPR] + PR) and clinical benefit rate (CR + VGPR + PR + minimal response [MR]) based on International Myeloma Working Group (IMWG) defined response criteria and the duration of response (DOR) in RRMM patients.
 - PFS and PFS at 6 months (PFS-6).
 - o OS.

4.3 Exploratory Objectives

- To characterize the expression of IL-3R/CD123 (and other potentially relevant markers) on MM cells, pDCs, and associated cell populations in peripheral blood (PB) and BM prior to and during/following therapy.
- To evaluate the treatment effects on IL-3R/CD123-expressing pDCs in the BM
 microenvironment prior to, during, and following therapy. Specifically, we will assess (i)
 the relative abundance of tumor cells to pDCs; (ii) immunohistochemistry (IHC) on BM
 biopsy specimens and flow cytometry analysis using antibodies specific against pDCs, to
 evaluate potential reduction in the pDC population in MM BM; and (iii) MM cell growthpromoting activity of pDCs will be determined by assessment of their ability to stimulate
 MM cell proliferation ex-vivo.
- To evaluate therapy-related effects on the levels of circulating cytokines/factors (i.e., IL-3
 and others) associated with pDCs and MM cell growth, survival, and immune
 dysfunction using serum and plasma samples prior to, during, and following therapy.

To identify surrogate markers of therapy-related anti-osteolytic activity. Specifically, we
will assess the levels of bone turnover markers (potentially to include N and C
teleopeptide, osteocalcin and bone alkaline phosphatase) prior to, during, and following
therapy.

5 Patient Selection

5.1 Study Population

The dose escalation stage phase 1 will require approximately 6 to 18 patients to evaluate 3 dose levels of SL-401/POM/DEX. In phase 2, 14 additional patients will be treated (20 total patients) at the MTD or maximum tested dose. Approximately 32 adult patients with RRMM who have previously received at least 2 prior lines of therapy for their disease may be enrolled in phase 1 and phase 2 of this study.

5.2 Patient Inclusion Criteria

Eligible patients will be considered for inclusion if they meet all of the following criteria. (All necessary baseline studies for determining eligibility must be obtained within 21 days or as indicated in the Schedule of Events [Table 13] prior to enrolment).

- Male or female patient who is at least 18 years of age.
- Patient has given voluntary written informed consent before performance of any studyrelated procedures not part of standard (non-investigational) medical care.
- 3. Patient has been previously diagnosed with MM based on standard criteria.
- Patient has received:
 - a. at least 2 prior therapies including a proteasome inhibitor (≥ 2 cycles) and lenalidomide (≥ 2 cycles), and
 - b. has achieved at least stable disease (SD) for ≥ 1 cycle of treatment on ≥ 1 prior treatment, and
 - has demonstrated disease progression subsequent to treatment, during or within 60 days following completion of the most recent therapy
- Patient has an Eastern Cooperative Oncology Group (ECOG) performance status score < 2.
- Patients has measurable disease defined as at least one of the following:
 - Serum monoclonal (M) protein ≥ 0.5 /dL (≥5 g/L).
 - b. Urine M protein ≥200 mg/24 hours.
 - c. Serum free light chain (FLC) assay: involved FLC ≥10 mg/dL (≥100 mg/L) and an abnormal serum FLC ratio (<0.26 or >1.65).
- Clinical Laboratory Inclusion Criteria: The following laboratory results must be met within 14 days prior to study drug (treatment) administration:
 - a. Absolute neutrophil count (ANC) ≥ 1000 cells/µl (growth factor cannot be used within the previous 7 days)
 - b. AST and ALT $\leq 2.5 \times$ upper limit of normal (ULN)
 - Platelet count ≥ 50,000/µl (without platelet transfusion in the previous 7 days)
 - d. Total bilirubin ≤ 1.5 mg/dL

- e. Serum creatinine ≤ 2.0 mL/dL and creatinine clearance ≥ 40 mL/min (calculated by the Cockcroft-Gault Equation or per 24 hour urine collection).
- f. Serum albumin $\geq 3.2 \text{ g/dL}$.
- g. Serum creatine phosphokinase (CPK) ≤ 2.5 × the ULN.
- h. Serum calcium (corrected for albumin) level at or below the ULN range (treatment of hypercalcemia is allowed and subject may enroll if hypercalcemia returns to normal range with standard treatment).
- Left ventricular ejection fraction (LVEF) ≥ institutional lower limit of normal as measured by multigated acquisition scan (MUGA) scan or 2-dimensional echocardiography (ECHO) within 28 days prior to start of therapy and no clinically significant abnormalities on a 12-lead electrocardiogram (ECG).
- 9. Females of childbearing potential (FCBP)* must have a negative serum or urine pregnancy test prior to initiation of the SL-401 Run-in Cycle and repeated with a sensitivity of at least 50 mIU/mL within 10 − 14 days prior to and again within 24 hours of starting POM and must either commit to continued abstinence from heterosexual intercourse or begin 2 acceptable methods of birth control, one highly effective method and 1 additional effective method at the same time, at least 28 days before she starts taking POM through 30 days after the last dose of POM and 60 days after the last dose of SL-401. FCBP must also agree to ongoing pregnancy testing during the entire duration of treatment. Men must agree to use a latex or synthetic condom during sexual contact with a FCBP even if they have had a vasectomy from the time of signing the informed consent form through 60 days after the last dose of POM or SL-401. These same patients must not donate sperm. All patients must be counseled at a minimum of every 28 days about pregnancy precautions and risks of fetal exposure. All patients enrolled into this study, must agree to be registered in and must comply with all requirements of the POM REMS™ program.

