- Clinical Laboratory Inclusion Criteria: The following laboratory results must be met within 14 days (or as stipulated) prior to study drug (treatment) administration:
 - a. Absolute neutrophil count (ANC) ≥ 1000 cells/µl (growth factor cannot be used within the previous 7 days).
 - Aspartate aminotransferase (AST) and alanine aminotransferase (ALT) ≤ 2.5 × upper limit of normal (ULN).
 - Platelet count ≥ 50,000/µl (without platelet transfusion in the previous 7 days).
 - d. Total bilirubin ≤ 1.5 mg/dL.
 - e. Serum creatinine ≤ 2.0 mL/dL and creatinine clearance ≥ 40 mL/min (calculated by the Cockcroft-Gault Equation or per 24 hour urine collection).

- Serum albumin ≥ 3.2 g/dL.
- g. Serum creatine phosphokinase (CPK) $\leq 2.5 \times$ the ULN.
- Serum calcium (corrected for albumin) level at or below the ULN range (treatment of hypercalcemia is allowed and subject may enroll if hypercalcemia returns to normal range with standard treatment).
- Left ventricular ejection fraction (LVEF) ≥ institutional lower limit of normal as measured by
 multigated acquisition scan (MUGA) scan or 2-dimensional echocardiography (ECHO) within 28 days
 prior to start of therapy and no clinically significant abnormalities on a 12-lead electrocardiogram
 (ECG).
- 9. Females of childbearing potential (FCBP)* must have a negative serum or urine pregnancy test prior to initiation of the SL-401 Run in Cycle (if required) and repeated with a sensitivity of at least 50 mIU/mL within 10 − 14 days prior to and again within 24 hours of starting POM and must either commit to continued abstinence from heterosexual intercourse or begin 2 acceptable methods of birth control, 1 highly effective method and 1 additional effective method at the same time, at least 28 days before she starts taking POM through 30 days after the last dose of POM and 60 days after the last dose of SL-401. FCBP must also agree to ongoing pregnancy testing during the entire duration of treatment. Men must agree to use a latex or synthetic condom during sexual contact with a FCBP even if they have had a vasectomy from the time of signing the informed consent form through 60 days after the last dose of POM or SL-401. These same patients must not donate sperm. All patients must be counseled at a minimum of every 28 days about pregnancy precautions and risks of fetal exposure. All patients enrolled into this study, must agree to be registered in and must comply with all requirements of the POM REMS™ program.

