6.4 Study Completion, Survival Extension Period, End-of-Study

The study is considered complete when sufficient information is available to enable assessment of the primary endpoint and selected secondary endpoints including response. In the weeks subsequent to a determination that sufficient information is available for these assessments, a date for database lock will be assigned, and any outstanding inquiries concerning data elements will be resolved. The Study Completion date will be the date beyond which study data is no longer entered into the primary database (this study completion date generally precedes the date on which the database lock occurs by several weeks/months).

In the event that patients continue to receive investigational therapy without evidence of MM progression at the time of Study Completion, an Extension Phase may be implemented in which investigational SL-401 will be made available. During this Extension Phase, investigators are encouraged to continue evaluation of patients (including laboratory and imaging assessments) at a schedule appropriate for MM patients receiving investigational therapy and POM/DEX. Data collection by the Sponsor during this Extension Phase will be limited to information pertaining to SL-401 administration, reason for SL-401 discontinuation, AEs (including serious adverse events [SAEs]), and survival status. This information will comprise a Supplemental Database. The End-of-Study (EOS) occurs approximately 30 days after the last patient has discontinued SL-401. In the event that no patients are receiving ongoing investigational SL-401 at time of primary database lock (Study Completion), then Study Completion and EOS will occur at approximately the same time.

The study duration for an individual patient will include a screening period for inclusion of up to 21 days, the treatment period may continue for 6 cycles of combination therapy or until disease progression, unacceptable adverse reaction or other reason for discontinuation. The administration of additional cycles of SL-401 > 6 cycles (not including the Run-in Cycle if received) must be discussed with the Medical Monitor at which time the individual patient's potential risk/benefit of further treatment will be assessed. After study drug discontinuation an end-of-treatment (EOT) visit will be done at 30 days to assess safety. Patients who discontinue

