7.2 Concomitant Therapies

7.2.1 Required Concomitant Therapies

- Pomalidomide increases the risk of thromboembolism. Anti-coagulation prophylaxis is required after an assessment of each patient's underlying risk factors, unless there is an excess risk of bleeding.
- FCBP must either commit to continued abstinence from heterosexual intercourse or begin 2 acceptable methods of birth control, 1 highly effective method and 1 additional effective method at the same time, at least 28 days before she starts taking POM through 30 days after the last dose of POM and 60 days after the last dose of SL-401. Men must agree to use a latex or synthetic condom during sexual contact with a FCBP even if they have had a vasectomy from the time of signing the informed consent form through 30 days after the last dose of POM and 60 days after the last dose of SL-401.
- All patients enrolled into this study, must be registered in and must comply with all requirements of the POMALYST REMS™ program.

Refer to Section 7.3.2.2 for premedications required before each SL-401 infusion.

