10.4 Pregnancy

A FCBP is a sexually mature female who: 1) has not undergone a hysterectomy or bilateral oophorectomy; or 2) has not been naturally postmenopausal for at least 24 consecutive months (i.e., has had menses at any time in the preceding 24 consecutive months).

FCBP must have a negative serum or urine pregnancy test prior to the first dose of SL-401 in the Run-in Cycle and FCBP must have a negative serum or urine pregnancy test prior with a sensitivity of at least 50 mIU/mL within 10 − 14 days prior to and again within 24 hours of starting SL-401/POM/DEX and must either commit to continued abstinence from heterosexual intercourse or begin 2 acceptable methods of birth control, 1 highly effective method and 1 additional effective method at the same time, at least 28 days before she starts taking SL-401/POM/DEX through 30 days after the last dose of POM and 60 days after the last dose of SL-401. FCBP must also agree to ongoing pregnancy testing during the entire duration of treatment. Men must agree to use a latex or synthetic condom during sexual contact with a FCBP even if they have had a vasectomy from the time of signing the ICF through 30 days after the last dose of POM and 60 days after the last dose of SL-401. These same patients must not donate sperm. All patients enrolled into this study, must be registered in and must comply with all requirements of the POMALYST REMS™ program.

Prior to study enrollment, FCBP must be advised of the importance of avoiding pregnancy during study participation and the potential risk factors for an unintentional pregnancy. This information will be included in the ICF that must be signed by the patient.

In addition, all FCBP or fertile men with partners of childbearing potential should be instructed to contact the Investigator immediately if they suspect they or their partner might be pregnant (e.g., missed or late menstrual period) at any time during study participation.

If following initiation of study drug, it is subsequently discovered that a patient is pregnant or may have been pregnant at the time of exposure to study therapy, including during at least 2 months after SL-401, study therapy will be permanently discontinued in an appropriate manner.

If a female partner of a male subject taking SL-401or POM becomes pregnant, the male subject should notify the Investigator immediately, and the pregnant female partner should be advised to call their healthcare provider immediately.

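### Men's contraception after pomalidomide is set at 60 days in inclusion criterion 9 but 30 days in Sections 7.2.1 and 10.4, and criterion 9 does not say which drug's last dose governs

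*Protocol*

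**What the plan says.** **Men.** Criterion 9 in Section 5.2 requires condom use from "signing the informed consent form through 60 days after the last dose of POM or SL-401". The synopsis version of the criterion has the same end point, "through 60 days after the last dose of POM or SL-401". Section 7.2.1 runs the requirement from "signing the informed consent form through 30 days after the last dose of POM and 60 days after the last dose of SL-401", and Section 10.4 from "signing the ICF through 30 days after the last dose of POM and 60 days after the last dose of SL-401". All four places are current, operative text, and the protocol gives no order of precedence.

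**Dosing that fixes the dates.** SL-401 is given on Days 1–5 of a 28-day cycle, and held infusions may run to Day 10. Pomalidomide is given on Days 1–21. From Cycle 7, Table 13 footnote u gives SL-401 in every other cycle only, while pomalidomide continues in each cycle.

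**Women of childbearing potential.** Those who do not commit to continued abstinence must begin two methods "at least 28 days before she starts taking POM" (criterion 9; Section 7.2.1 agrees). Section 10.4 counts the same 28 days back from SL-401/POM/DEX. Section 6.4 describes a "screening period for inclusion of up to 21 days", and Section 6.2.4 drops the Run-in Cycle in phase 2.

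**The concern.** What a man agrees to at eligibility is not what the treatment and pregnancy sections tell the site to apply. The stop date he is given depends on which section the site consults. If the site uses criterion 9, it also depends on how *or* is read. The subject is fetal exposure to a drug that every patient must take under a REMS program, so the documents should give one answer. No endpoint, dose-limiting-toxicity rule or analysis depends on it.

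The women's lead-in raises a lesser question. In phase 2 pomalidomide starts on Day 1 of the first cycle, while the required lead-in of 28 days is longer than the 21-day screening window.

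**Working it through.** The protocol gives no calculated figure here to reproduce. The check sets the rules side by side and counts days.

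**Inputs.** Days are counted from Day 1 of the last cycle, with 28-day cycles. S is the day of the last SL-401 dose and P the day of the last pomalidomide dose.

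**Formulas**
- Criterion 9, later-dose reading: max(S, P) + 60
- Criterion 9, earlier-dose reading: min(S, P) + 60
- Sections 7.2.1 and 10.4, both conditions met: max(P + 30, S + 60)

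**Results**

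| Last cycle | S | P | Criterion 9, later | Criterion 9, earlier | 7.2.1 / 10.4 |
|---|---|---|---|---|---|
| Both drugs on schedule | 5 | 21 | 21 + 60 = 81 | 5 + 60 = 65 | max(51, 65) = 65 |
| Infusions run to Day 10 | 10 | 21 | 21 + 60 = 81 | 10 + 60 = 70 | max(51, 70) = 70 |
| Cycle 7 onward, cycle without SL-401 | 5 − 28 = −23 | 21 | 21 + 60 = 81 | −23 + 60 = 37 | max(51, 37) = 51 |

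**Differences on the later-dose reading:** 81 − 65 = 16 days, 81 − 70 = 11 days and 81 − 51 = 30 days. When pomalidomide outlasts SL-401 by d days, the gap is the smaller of d and 30. It therefore reaches 30 only when d is at least 30; in the third row d = 21 − (−23) = 44. If pomalidomide stops on or before the last SL-401 dose, both rules give S + 60 and the gap is zero.

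**Differences on the earlier-dose reading:** none in the first two rows. In the third row criterion 9 ends 51 − 37 = 14 days *before* Sections 7.2.1 and 10.4.

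**Women, phase 2.** A woman who first begins two methods at Day −21 has at most 21 days before pomalidomide on Day 1, which is 28 − 21 = 7 days short. In phase 1 the 28-day Run-in Cycle covers the lead-in before pomalidomide. It does not cover it if Section 10.4 is read as counting back from the first SL-401 dose.

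**The case against.** **The practical gap for men is smaller than 60 against 30 suggests.** This stands. Sections 7.2.1 and 10.4 also require 60 days after SL-401, which brings the difference to 16 or 11 days when both drugs end in the same cycle as scheduled. A reader might infer that the rules diverge in every cycle. They do not: the end date depends on each drug's last dose, and Table 11 lets pomalidomide be held, omitted or discontinued, so it can stop first.

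**On the later-dose reading criterion 9 is never the shorter rule, so following it satisfies the other sections too.** This is true on that reading only. On the earlier-dose reading criterion 9 can be the shorter rule, and the protocol does not say which reading is meant.

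**The REMS program applies in any case.** The protocol does require compliance, but its terms are not in the document. The text therefore cannot settle which interval applies, nor show that either one leaves fetal exposure uncontrolled.

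**A reader might also infer that criterion 9 ends the sperm-donation ban at 60 days.** It does not. The ban is a separate sentence with no end date.

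**The strongest objection concerns women.** A reader might infer that the 28-day lead-in contradicts the 21-day screening window and that such women cannot enter phase 2. The protocol does not support this. Section 5.2 applies the 21 days to baseline studies for eligibility. Section 9.1 lists consent within Day −21 to −1, but Table 13 footnote a places it before screening. Continued abstinence, existing use of two methods, or starting before Day −21 would each comply. What remains is a feasibility gap for a woman who is not abstinent, is not already using two methods, and first begins them inside the window. The protocol does not say how many of the 14 additional phase 2 patients that might be.

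**Conclusion.** The inconsistency for men holds: four operative places give two different post-pomalidomide intervals, and criterion 9 does not identify the governing dose. On the later-dose reading criterion 9 ends 16 days later than Sections 7.2.1 and 10.4 in a usual last cycle, 11 days later if infusions run to Day 10, and 30 days later when the last cycle has no SL-401. On the earlier-dose reading there is no gap in the usual cycle and a 14-day gap in the opposite direction in a cycle without SL-401. These figures assume pomalidomide through Day 21, 28-day cycles without delay and, for the third case, SL-401 last given on Day 5 of the preceding cycle.

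The women's lead-in is a secondary note only. It is a possible 7-day shortfall in phase 2 for those first starting contraception in the screening window, plus a difference in the reference point (pomalidomide in criterion 9 and Section 7.2.1; SL-401/POM/DEX in Section 10.4). No view is taken on which interval is right.

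**What to change.** Reconcile criterion 9 (synopsis and Section 5.2) with Sections 7.2.1 and 10.4 so that a single end rule for male contraception appears in every place and in the consent form. The rule should state explicitly which drug's last dose governs. The interval is for the sponsor and the REMS requirements to set.

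In the same revision, reconcile the women's passages. Use one reference point for the 28-day lead-in in criterion 9 and Sections 7.2.1 and 10.4, and make clear how that lead-in relates to consent and the Day −21 to −1 window when there is no Run-in Cycle.

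The cost is protocol and consent wording only. Sample size and analyses are unaffected.
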